2.2.1 FLUDROCORTISONE ACETATE

Fludrocortisone acetate (9- α -Fluoro-11 β . 17 α , 21-trihydroxy-4-pregnene-3, 20 dione acetate) is a synthetic steroid possessing a potent mineralocorticoid effect and a high glucocorticoid activity [19]. FCA is a synthetic corticosteroid with anti-inflammatory and anti-allergic properties. FCA is a mineralocorticoid receptor and glucocorticoid receptor agonist that binds to cytoplasmic receptors, translocates to the nucleus and subsequently initiates the transcription of glucocorticoid-responsive genes such as

lipocortins to inhibit phospholipase A2. This prevents the release of arachidonic acid, a precursor to prostaglandins and leukotrienes, both important mediators in the pro-inflammatory response mechanism. In addition, this agent exerts its mineralocorticoid effect on the distal tubules and collecting ducts of the kidney by inducing permease, an enzyme that regulates Na⁺ permeability in cells, thereby enhancing Na⁺ reabsorption and water retention as well as increasing K⁺, H⁺ excretion.

2.2.2 CLINICAL DATA

This section is intended to briefly summarise the information on characteristics and safety of Fludrocortisone acetate relevant for the present study. For complete and detailed information refer to the Investigator's Brochure.

The safety and tolerability of oral Fludrocortisone acetate has been determined by a number of clinical studies. Fludrocortisone acetate has been used in the treatment of cerebral salt wasting syndrome [20-22]. It is used primarily to replace the missing hormone aldosterone in various forms of adrenal insufficiency such as Addison's disease and the classic salt wasting (21-hydroxylase deficiency) form of congenital adrenal hyperplasia [23-25]. Due to its effects on increasing Na⁺ levels, and therefore blood volume, fludrocortisone acetate is the first line of treatment for orthostatic intolerance and postural orthostatic tachycardia syndrome (POTS) [26-28]. It can be used to treat low blood pressure.

Fludrocortisone acetate is also a confirmation test for diagnosing Conn's syndrome (aldosterone producing-adrenal adenoma), via the fludrocortisone suppression test. Loading the patient with fludrocortisone would suppress serum aldosterone level in a normal patient, whereas the level would remain elevated in a Conn's patient [29]. The fludrocortisone suppression test is an alternative to the NaCl challenge (which would use normal saline or NaCl tablets).

2.2.3 ANIMAL STUDIES

An animal study was conducted to evaluate the safety and efficiency of Fludrocortisone acetate after intravitreal injection into the vitreous cavity [30]. Surgeries were performed on the eyes of 25 New Zealand white rabbits. Fludrocortisone acetate was titrated using sterile BSS solution to the following concentrations: 4 mg/ 0.1 ml, 2 mg/ 0.1 ml, 1 mg/0.1 ml, and 400 µg/0.1 ml, which were injected intravitreal into one eye of twenty-five rabbit eyes. The control eyes received 0.1 ml of sterile BSS. All animals were examined before and after injection using indirect ophthalmoscope and slit-lamp biomicroscopy. Electroretinography (ERG) was performed on all animals prior to intravitreal injection and two weeks after injection. The animals were re-examined at this time by indirect ophthalmoscope and slit-lamp biomicroscopy and were euthanized. Their eyes were enucleated and examined with light microscopy.

Outcomes from these in vivo tests were positive for the application of intravitreal Fludrocortisone acetate. In multiple measurements, up to 40 days of observations, the slit lamp biomicroscopy and indirect ophthalmoscopy did not show any evidence of significant inflammation in the anterior or posterior segment of the eye in either the control or treatment groups. Intraocular pressure (IOP) was normal across all groups. Histological examination of retinal sections, under light microscopy, revealed that the integrity of the retinal layers appeared preserved with no evidence of toxicity or vacuolization except for one eye in the 4mg group. All aggregates of Fludrocortisone acetate disappeared by 22 +/-8 days in the 2-mg group, and 33 +/-7 days in the 4-mg group.

In ERG testing, one eye injected with 4mg/0.1ml exhibited decreases in ERG output. All other eyes had a normal ERG. These findings represent promising results for intravitreal Fludrocortisone acetate that is clinically suitable for both short-term and long-term use.

Data from the light-damage model of dry AMD in mice showed FCA delivered in Kenalog vehicle resulted in significantly less cell death, and significantly fewer macrophages that carry the IBA1 marker 7 days later. Histology shows that the animals

treated with FCA have a much thicker outer nuclear layer. Treated animals have a significantly more robust Electroretinogram A-wave (Photoreceptor function) and B-wave (inner retinal function).

2.3 RATIONALE

2.3.1 RATIONALE FOR THIS STUDY

Fludrocortisone acetate is available in tablet form (0.1 mg) from the PBS and so is approved for use in humans in Australia. In a study of 121 patients Gonzalez [31] reported excellent outcomes with fludrocortisone for anterior segment lesions. He cited 4 previous papers with similar experiences.

There is older pre-clinical data suggesting FCA is effective. Among that is Fitzgerald et al. [32] who found that FCA was superior to TA in a study of phorbol-12-myristate-acetate (PMA)-stimulated monkey choroidal endothelial cells (CECs) in restoring quiescent morphology and reducing membrane permeability. [name] et al. have a large body of new preclinical data that indicates FCA is superior to TA in a rat model of dry AMD. FCA was superior in terms of preventing cell death, macrophage recruitment, and preserving a- and b-wave ERG amplitude.

Kivilcim [33] examined intravitreal FCA in 25 normal rabbits at 4 mg/0.1 ml, 2 mg/0.1 ml, 1 mg/0.1 ml, and 400 µg/0.1 ml. Two eyes at 4 mg/0.1 ml experienced intravitreal haemorrhage and reduced ERG. There were no other problems of reductions in ERG. The smaller volume of the rabbit eye would suggest 4 mg/0.1 ml would be safe in humans. TA is commonly given at 4 mg/0.1 ml so comparing the same doses for each steroid would be sensible.

In the current clinical study fludrocortisone acetate, corticosteroid inhibiting complement activation will be administered to patients with GA. The goal of the study is to assess

the safety and tolerability of single dose IVT Fludrocortisone acetate. Results from this study will guide decisions to further develop intravitreal Fludrocortisone acetate for GA.

2.3.2 DOSE SELECTION

A single dose of 1mg/0.1mL or 2mg/0.1mL injection administered once will be tested in this study (see Section 5.2.1). Intravitreal fludrocortisone acetate was well-tolerated in a panel of animal toxicology studies. The volume of the human vitreous is approximately 4 mL, which is approximately 2.7-fold larger than the mean vitreous volume of rabbits, 1.5mL. Based on the difference in vitreous volume between man and rabbit, the human equivalent dose was determined to be 67 mg/eye every 4 weeks. The dose (1- or 2mg/0.1 mL injection) of Fludrocortisone acetate that will be evaluated in this clinical study is expected to result in drug concentrations approximately 1.3 fold lower than observed in rabbits.

2.3.3 RISK/BENEFIT

The safety monitoring practices employed by this protocol (e.g. complete ophthalmologic exam, IOP monitoring, OCT, vital signs, hematology, serum chemistry, and AE questioning) are adequate to protect the subjects' safety.

There are risks associated with the ophthalmic procedures required for participants in this study. However, these are all standard procedures that are widely performed in ophthalmology.

In the days following any IVT injection, patients are at risk of developing endophthalmitis. If the eye should become red, sensitive to light, painful, or develop a change in vision, the patient will be instructed to seek immediate care from an ophthalmologist. Other risks of IVT injection include traumatic cataract, retinal detachment and hemorrhage.

Transient increased IOP has also been identified as a risk following IVT injections. IOP will be carefully monitored in this study.

The approximately 150 mL of blood (See Section 9.9) planned for collection from each subject over the 6 months of the study does not pose an undue risk in this patient population.

Based on data available to date, IVT administration of Fludrocortisone acetate does not seem to present an unreasonable ophthalmic or systemic risk in animal models. Fludrocortisone acetate has been safely used systemically as mineralocorticoid replacement for severe orthostatic hypotension in Addison's disease and other salt-water imbalances.

However, as Fludrocortisone acetate has not been used intravitreally in human participants there are potential unforeseen risks. To mitigate such risks, this study is being conducted in two parts, restricting treatment to a single individual together with extended assessment, prior to application in other participants. Numerous follow-up visits and numbers of testing procedures have also been instituted in the assessment schedule for all participants to ensure adverse events, or other safety issues that arise are identified and addressed in a timely manner.

There is a potential health benefit for trial participants from receipt of study drug. We propose to administer intravitreal Fludrocortisone acetate to patients with GA. If efficacious, intravitreal Fludrocortisone acetate is expected to alter the course of GA and slow its rate of progression.

3 OBJECTIVES AND ENDPOINTS

3.1 STUDY OBJECTIVES

The primary objectives of the study are to assess the safety and tolerability of IVT injections of Fludrocortisone acetate in subjects with GA associated with Age-Related Macular Degeneration in order to support further development into confirmatory Phase II studies.

3.2 STUDY ENDPOINTS

3.2.1 PRIMARY SAFETY ENDPOINT

To demonstrate safety and tolerability of IVT injections of Fludrocortisone acetate based upon the mean change in GA lesion size as measured by Fundus Autofluorescence (FAF).

- Number and severity of local and systemic treatment emergent adverse events.
-

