15. Participation in another interventional clinical study, or use of any experimental treatment for AMD or any other investigational new drug within 6 weeks or 5 half-lives of the active (whichever is longer) prior to the start of study treatment. Note: clinical trials solely involving observation, over-the-counter vitamins, supplements, or diets are not exclusionary.
16. Systemic conditions that are applicable to the use of fludrocortisone such as hypertension, and fungal infections.
17. Medical or psychiatric conditions that, in the opinion of the investigator, make consistent follow-up over the study period unlikely, or in general a poor medical risk because of other systemic diseases or active uncontrolled infections.
18. Any screening laboratory value (haematology, serum chemistry or urinalysis) that in the opinion of the investigator is clinically significant and not suitable for study participation.
19. Hypersensitivity to fluorescein.

Endpoints: The primary endpoints of the study are safety and tolerability of intravitreal (IVT) dose of Fludrocortisone acetate in subjects with geographic atrophy (GA) secondary to Age-Related Macular Degeneration (AMD), based on assessment of vital signs, clinical safety labs, and adverse events.

Primary Safety Endpoint

- Number and severity of local and systemic treatment emergent events (TEAE).

Secondary Endpoints

- The change in geographic atrophy (GA) lesion size from baseline to Month 6 as measured by FAF.
- Change in best corrected visual acuity (BCVA).
- Change in low luminance best corrected visual acuity (LL-BCVA).
- Relationship between GA lesion size changes and changes in BCVA.
- Increase in intraocular pressure (IOP).

Pharmacokinetic (PK) parameters

- Exposure after single dose Fludrocortisone acetate IVT injections.
- Serum maximum observed concentration.
- Time to maximum measured concentration
- Terminal elimination half-life.

- Planned Interim Analysis** There is no formal interim analysis planned for this study. However, a data safety monitoring board (DSMB) for safety data review will be planned for this study.
- Analysis Populations** The following analysis populations are planned:
- **Safety Population:** All enrolled participants IVT Fludrocortisone acetate will be included in the safety population.

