3.2.2 SECONDARY ENDPOINTS

- The change in square root geographic atrophy (GA) lesion size from baseline to Month 6 as measured by FAF.
- Change in best corrected visual acuity (BCVA).
- Change in low luminance best corrected visual acuity (LL-BCVA).
- Relationship between GA lesion size changes and changes in BCVA.
- Change in vital signs.

- Increase in intraocular pressure (IOP).

Pharmacokinetic (PK) parameters

- Exposure after single dose Fludrocortisone acetate IVT injections.
- Serum maximum observed concentration.
- Time to maximum measured concentration
- Terminal elimination half-life.

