8.3 ANALYSIS OF PRIMARY SAFETY ENDPOINTS

No formal inferential statistics will be performed on safety assessments. Statistical methods for the safety analyses will be primarily descriptive in nature. The Fludrocortisone acetate 1mg/0.1mL and 2mg/0.1 mL injection will be considered as safe and tolerable based on the number of subjects presenting severe AEs related to the study drug. It is understood that safety is a medical judgment that cannot be prospectively defined in detail. However, as general guidance, a subject will be considered to have tolerated a dose if the subject experiences no clinically significant drug-related adverse event or laboratory abnormality. Conversely, a subject will not be considered to have tolerated the dose if he experiences a clinically significant drug-related adverse event or laboratory abnormality during the study drug administration or post-administration follow-up period.

Listings and summaries for all safety data will be presented using the Safety Population. Descriptive statistics (mean, SD, median, minimum and maximum) will be calculated for summaries of continuous safety data and frequency counts and percentages (where appropriate) will be calculated for summaries of discrete/categorical safety data.

Adverse events (AEs) will be coded using the Medical Dictionary for Regulatory Activities (MedDRA), and data will be summarised by System, Organ, Class and preferred term. The number and percent of participants reporting each AE will be summarised descriptively (n=9). A participant with two or more AEs within the same level of summarisation (i.e., system, organ, class or preferred term) will be counted only once in that level. The number of AEs reported will also be presented. Adverse events will also be summarised by severity as well as relationship to study treatment. A by-participant AE data listing, including verbatim term, preferred term, system organ class, severity, and relationship to study treatment, will be provided. Separate listings will be generated for SAEs and AEs leading to study/treatment discontinuation.

All haematology, blood chemistry and urinalysis (continuous variables) parameters will be summarised using descriptive statistics for all study visits assessed, including change from baseline (last pre-surgery value) for all post-surgery assessments. All laboratory data will be included in the data listings and all test values outside the normal range will be flagged.

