8.4 ANALYSIS OF SECONDARY ENDPOINTS

The efficacy endpoints are the secondary endpoints of this study, which include complete ocular examination.

ETDRS best-corrected visual acuity (BCVA) will be scored with reference to the Early Treatment Diabetic Retinopathy Study ETDRS letters). ETDRS will be treated as continuous data, and descriptive statistics (mean, SD, median, minimum and maximum) will be summarised for ETDRS observed value and change from baseline at each post-

surgery visit. Exploratory analysis of ETDRS change over time will be assessed by using a mixed model. The correlations between repeated measures of the same participant will be accounted for by the mixed model. The least squares mean of ETDRS change from baseline and its 95% confidence interval at each visit will be estimated. Similar analyses will be conducted for intraocular pressures. Categorical efficacy endpoints such as slit lamp biomicroscopy exam findings, dilated ophthalmoscopy exam findings, color fundus photography and OCT finding will be summarised descriptively by frequency count and percentage (proportion) where appropriate.

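### Section 3.2.1 rests the primary safety endpoint on mean change in GA lesion size, an efficacy measure, so the primary endpoint is defined inconsistently; 8.3 should also report adverse events by dose

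*Protocol*

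**What the plan says.** Protocol 3.2.1, Primary Safety Endpoint, opens: "To demonstrate safety and tolerability of IVT injections of Fludrocortisone acetate based upon the mean change in GA lesion size", measured by fundus autofluorescence. The only bullet beneath it is different: "Number and severity of local and systemic treatment emergent adverse events".

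The synopsis (1.1, Endpoints) says the primary endpoints are safety and tolerability "based on assessment of vital signs, clinical safety labs, and adverse events". Its primary safety endpoint is "Number and severity of local and systemic treatment emergent events (TEAE"), and lesion-size change heads its secondary list. Section 3.2.2 also lists lesion size as secondary: "The change in square root geographic atrophy (GA) lesion size from baseline to Month 6 as measured by FAF". Section 8.4 gives the class of these endpoints: "The efficacy endpoints are the secondary endpoints of this study, which include complete ocular examination".

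Section 8.3, Analysis of Primary Safety Endpoints, covers adverse events, laboratory values, vital signs and physical examinations. It says the two injections "will be considered as safe and tolerable based on the number of subjects presenting severe AEs related to the study drug". As general guidance, it then says that a subject has not tolerated a dose after any drug-related adverse event or laboratory abnormality judged clinically significant. On reporting it says: "The number and percent of participants reporting each AE will be summarised descriptively (n=9").

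**The concern.** A primary endpoint should be stated once and mean the same thing wherever it appears. Here the section that defines it ties safety to a measure that the rest of the protocol treats as evidence of benefit. Section 2.3.3 names slower progression as the hoped-for effect.

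Mean lesion change cannot carry a safety conclusion in this design. Section 2.2 describes GA as progressive, and there is no control arm. Growth in treated eyes therefore does not separate drug harm from natural history. Slow growth says nothing about inflammation, raised pressure or haemorrhage.

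The label also determines who is analysed. Section 8.1 assigns safety endpoints to everyone dosed, and efficacy endpoints to those with a visit at or after Month 2. Lesion size currently falls under both headings.

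The single denominator in 8.3 raises a related question. The objective is the safety of each of two doses, but no summary by dose is stated.

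**Working it through.** **1. The endpoint passages side by side**

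| Place | Role of lesion size | What carries primary safety |
|---|---|---|
| 1.1 Synopsis, Endpoints | Secondary, area, to Month 6 | Treatment-emergent events; basis is vital signs, labs and AEs |
| 3.2.1 lead sentence | Basis of safety; no scale or time point | Lesion size |
| 3.2.1 bullet | None | Treatment-emergent AEs |
| 3.2.2 | Secondary, square root, to Month 6 | Not applicable |
| 7.11.3 | Growth that is unequivocal progression is not recorded as an AE | Not applicable |
| 8.3 | Not used | AEs, labs, vital signs, physical examination |
| 8.4 and synopsis efficacy analysis | Efficacy | Not applicable |

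Only the lead sentence of 3.2.1 gives lesion size a safety role. Section 7.11.3 works against that role, because it keeps unequivocal lesion growth out of the adverse event record. The lead sentence is the outlier, and the bullet below it agrees with the synopsis and with 8.3.

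**2. Vital signs and laboratory tests**

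The synopsis makes both part of the basis of the primary endpoint. Section 3.2.2 lists change in vital signs as secondary and does not mention laboratory tests. Section 8.3 analyses both under primary safety. Their place is therefore not settled either.

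**3. The two tolerability sentences in 8.3**

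Under 7.10.4.1, severe means Grade 3. A drug-related Grade 2 event judged clinically significant would mean that the subject had not tolerated the dose under the second sentence, but it would not count under the first.

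**4. The denominator in 8.3**

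Inputs from the synopsis: 3 participants planned at 1 mg/0.1 mL and 6 at 2 mg/0.1 mL.

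- Reproducing the stated figure: 3 + 6 = 9, so the n=9 in 8.3 is both cohorts together.
- Illustration A (assumed counts): two participants with an event, both at 2 mg. By dose, 0/3 = 0% and 2/6 = 33.3%. Overall, 2/9 = 22.2%.
- Illustration B (assumed count): one participant with an event, at 1 mg. By dose, 1/3 = 33.3% and 0/6 = 0%. Overall, 1/9 = 11.1%.

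An event confined to one dose is diluted by 6/9 if it occurs at 2 mg and by 3/9 if it occurs at 1 mg. The written 9 also fails to match the number treated if enrolment stops early under 6.2, or if it reaches the 12 allowed by 8.6.

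**The case against.** The strongest reply is that the trial would still be analysed correctly. The adverse event bullet stands directly under the faulty sentence, the synopsis gives it as the only primary endpoint, and 8.3 analyses it. A reader might infer that the primary question goes unanswered, and the documents do not support that. This reply stands, and it limits the point to an inconsistent definition.

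A reader might also infer that a toxic dose could pass, or an inactive but safe one fail, on lesion growth. That would need a rule that uses lesion size, and there is none. No threshold or test is set, the escalation and stopping text (1.1, 5.2.1, 6.2) uses dose-limiting toxicity and drug-related events, and lesion size is not among the review criteria named for the DSMB (9.7). This also stands.

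Accelerated atrophy could in principle be a harm, so lesion size is not absurd as a safety signal. Reading it that way would need a comparator. The fellow eye is imaged at screening and Day 150 (6.3.1, 6.3.5), but Section 8 plans no comparison with it. The defence does not rescue the sentence.

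On the denominator, 8.3 uses the Safety Population and 8.1 defines it as everyone dosed, so participants treated is already the governing rule and (n=9) reads as the planned total. Pooling is inferred from that parenthesis, because 8.3 never says that doses are combined. By-participant listings are planned, the first subject in each cohort is reviewed before the rest are recruited, and a by-dose layout may sit in an analysis plan that is not shown. All of this stands, so it would be wrong to say the plan hides the dose relation. Stating the by-dose display is a clarification.

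The two tolerability sentences work partly at different levels, one for the injection and one for the single subject. That softens the conflict, but the protocol does not say how the subject-level judgement feeds the dose-level one.

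**Conclusion.** The lead sentence of 3.2.1 is wrong as written. It bases safety on a measure that the synopsis, 3.2.2 and 8.4 treat as secondary and efficacy, that 7.11.3 keeps out of adverse events when it reflects unequivocal progression, and that 8.3 does not use. This rests on the text alone and has no numerical size. The consequence is two competing definitions of the primary endpoint, with two possible analysis populations for lesion size. Reading the adverse event bullet as the intended endpoint rests on its agreement with the synopsis and 8.3.

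The by-dose point is secondary. Its size, 33% against 22% for two events at 2 mg, depends on assumed counts and on the planned cohorts of 3 and 6. It would arise only if the overall column were the only one shown.

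**What to change.** - **3.2.1:** delete the lesion-size clause. Keep lesion-size change as a secondary endpoint only, on one scale (the synopsis gives area, 3.2.2 gives square root).
- **1.1, 3.2.1 and 8.3:** state the primary endpoint in identical words, as the count and severity of treatment-emergent adverse events, local and systemic. Say once whether vital signs and laboratory tests belong to the primary assessment or are secondary, and align 3.2.2.
- **8.3, reporting:** replace (n=9) with participants treated, and give counts and percentages by dose level (planned 3 and 6) as well as overall.
- **8.3, tolerability:** reconcile the sentence on severe drug-related events with the sentence on clinically significant ones, and say how the subject-level judgement informs the judgement on each dose.

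A new dose-limiting-toxicity endpoint and exact binomial limits are not required, because the study is descriptive by design. The difference between 9 and up to 12 participants (synopsis and Section 4 against 8.6) needs reconciling as a separate matter.

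The cost is a wording amendment to four sections, with the prior IRB/IEC approval that 10.1 requires. No assessment, visit or data item changes, and the extra table columns use data already collected.
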